5.1 Phase: I vs. II

6.0 Registration/Randomization Procedures

6.1 Phase I

Prior to discussing protocol entry with the patient, call the MCCC Registration Office for dose level and to insure that a place on the protocol is open to the patient.

- 6.11 Registration Procedures
 - 6.111 To register a patient, fax (**MCCC**) a completed eligibility checklist to the Mayo Clinic Cancer Center (MCCC) Registration Office between 8 a.m. and 4:30 p.m. central time Monday through Friday.

6.2 Phase II

- 6.21 Registration Procedures
 - 6.211 To register a patient, access the Mayo Clinic Cancer Center (MCCC) web page and enter the registration/randomization application. The registration/randomization application is available 24 hours a day, 7 days a week. Back up and/or system support contact information is available on the Web site. If unable to access the Web site, call the MCCC Registration Office at the between the hours of 8 a.m. and 5:00 p.m. Central Time (Monday through Friday).

The instructions for the registration/randomization application are available on the MCCC web page and a state of the process for completing and confirming patient registration. Prior to initiation of protocol treatment, this process must be completed in its entirety and a MCCC subject ID number must be available as noted in the instructions. It is the responsibility of the individual and institution registering the patient to confirm the process has been successfully completed prior to release of the study agent. Patient registration via the registration/randomization application can be confirmed in any of the following ways:

- Contact the MCCC Registration Office **Determined**. If the patient was fully registered, the MCCC Registration Office staff can access the information from the centralized database and confirm the registration.
- Refer to "Instructions for Remote Registration" in section "Finding/Displaying Information about A Registered Subject."

- 6.3 Phase I and II
 - 6.31 Correlative Research

Mandatory:

A mandatory correlative research component is part of this study, the patient will be automatically registered onto this component (see Sections 3.19e and 14.0).

Optional:

An optional correlative research component is part of this study, there will be an option to select if the patient is to be registered onto this component (see Sections 14.0 and 17.0).

- Patient has/has not given permission to give his/her bone marrow aspirate sample for research testing.
- Patient has/has not given permission to give his/her lymph node aspirate or biopsy sample for research testing.
- 6.32 Prior to accepting the registration, registration/randomization application will verify the following:
 - IRB approval at the registering institution
 - Patient eligibility
 - Existence of a signed consent form
 - Existence of a signed authorization for use and disclosure of protected health information
- 6.33 Documentation of IRB approval must be on file in the Registration Office before an investigator may register any patients.

In addition to submitting initial IRB approval documents, ongoing IRB approval documentation must be on file (no less than annually) at the Registration Office (fax: **Constitution**). If the necessary documentation is not submitted in advance of attempting patient registration, the registration will not be accepted and the patient may not be enrolled in the protocol until the situation is resolved.

When the study has been permanently closed to patient enrollment, submission of annual IRB approvals to the Registration Office is no longer necessary.

- 6.34 At the time of registration, the following will be recorded:
 - Patient has/has not given permission to store and use his/her sample(s) for future research of CLL at Mayo.
 - Patient has/has not given permission to store and use his/her sample(s) for future research to learn, prevent, or treat other health problems.
 - Patient has/has not given permission for MCCC to give his/her sample(s) to researchers at other institutions.
- 6.35 Treatment on this protocol must commence at Mayo Clinic in Florida under the supervision of a medical oncologist or hematologist.

- 6.36 Treatment cannot begin prior to registration and must begin \leq 7 days after registration.
- 6.37 Pretreatment tests/procedures (see Section 4.0) must be completed within the guidelines specified on the test schedule.
- 6.38 All required baseline symptoms (see Section 10.6) must be documented and graded.
- 6.39 Study drug is available on site.

7.0 **Protocol Treatment**

- 7.1 Treatment Schedule Cycle length = 28 days Cycles 1-11; Cycle length = 49-56 days Cycle 12 (or last cycle of treatment if patient discontinues treatment before Cycle 12)
 - 7.11 Phase I (Dose Escalation)

Cycle 1

| Agent | Dose | Route | Day |
|--------------|--|-------|------|
| Lenalidomide | As assigned by Registration Office | Oral | 1-21 |

Cycles 2-12*

| Cycles - | | | |
|--------------|--|-------|------|
| Agent | Dose | Route | Day |
| Lenalidomide | Assigned at time of registration | Oral | 1-21 |
| AT-101 | Assigned at time of registration | Oral | 1-3 |

*Growth factors cannot be used during Cycle 2 due to DLT monitoring.

7.12 Phase II

Cycle 1

| Agent | Dose | Route | Day |
|--------------|-----------------------------|-------|------|
| Lenalidomide | MTD per Phase I findings | Oral | 1-21 |

Cycles 2-12

| Agent | Dose | Route | Day |
|--------------|---------------|-------|------|
| Lenalidomide | MTD per Phase | Oral | 1-21 |
| | I findings | | |
| AT-101 | MTD per Phase | Oral | 1-3 |
| | I findings | | |

- 7.2 Phase I determination of Maximum Tolerated Dose (MTD)
 - 7.21 Dose Escalation

| Dose level | Lenalidomide | AT-101 |
|------------|--------------|--------------|
| -2 | 5 mg | 20 mg b.i.d. |
| -1 | 5 mg | 30 mg b.i.d. |
| *1 | 5 mg | 40 mg b.i.d. |
| 2 | 10 mg | 40 mg b.i.d. |
| 3 | 15 mg | 40 mg b.i.d. |
| 4 | 20 mg | 40 mg b.i.d. |

^{*}starting dose level

- 7.211 Treatment by a local medical doctor is not allowed.
- 7.212 Three patients will be treated at each dose level and observed during the first cycle of the combination therapy (i.e., cycle 2: lenalidomide and AT-101, up to day 28 of starting the combination) to assess toxicities, before new patients are treated. Doses will not be escalated in any individual patient.
- 7.213 Investigators are to contact the Study Chair as soon as any dose-limiting toxicity (DLT) occurs.

7.22 Definitions of DLT

7.221 For this protocol, dose-limiting toxicity (DLT) will be defined as an adverse event at least possibly related to treatment (definitely, probably, or possibly related) that occurs in cycle 2 of the study treatment and meets the following criteria:

| Toxicity | DLT Definition |
|-----------------|--|
| Hematologic | ANC $\leq 0.5 \times 10^{9}$ /L for more than 14 |
| - | days |
| | Febrile neutropenia of any duration |
| | $(ANC < 1.0 \text{ x } 10^{9}/\text{L}, \text{ fever} \ge 38.5^{\circ}\text{C})$ |
| | Grade 4 thrombocytopenia or Grade |
| | 3 thrombocytopenia with bleeding or |
| | any requirement for platelet |
| | transfusion |
| | Grade 4 anemia, unexplained by |
| | underlying disease |
| Non-hematologic | Any grade 3 or 4 (except tumor lysis |
| | syndrome, tumor flare reaction, |
| | fatigue, nausea, hyperglycemia in |
| | diabetic patients) |

| Dose Level | Lenalidomide | AT-101 |
|---------------|--------------|--------------|
| -2 | 5 mg | 20 mg b.i.d. |
| -1 | 5 mg | 30 mg b.i.d. |
| 1* | 5 mg | 40 mg b.i.d. |
| 2 | 10 mg | 40 mg b.i.d. |
| 3 | 15 mg | 40 mg b.i.d. |
| 4 | 20 mg | 40 mg b.i.d. |

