2.0 Goals

- 2.1 Primary
 - 2.11 Phase I: Determine the maximum tolerated dose (MTD) of lenalidomide in combination with AT-101.
 - 2.12 Phase II: To assess the overall response rate of lenalidomide in combination with AT-101.
- 2.2 Secondary
 - 2.21 To assess the overall response rates of lenalidomide in combination with AT-101 at 6 months and 12 months.
 - 2.22 To evaluate time to progression (TTP) for the combination of lenalidomide + AT-101.
 - 2.23 To evaluate the safety of this combination in patients with relapsed B-CLL.
- 2.3 Correlative Research
 - 2.31 To conduct correlative studies for further understanding of the mechanism of antitumor activity of lenalidomide and lenalidomide + AT-101.

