8.2 Lenalidomide

A new course of treatment may begin on the scheduled Day 1 of a new cycle if:

- The ANC is $\geq 1,000/\mu$ L;
- The platelet count is $\geq 25,000/\mu$ L;
- Any lenalidomide-related allergic reaction/hypersensitivity or sinus bradycardia/ other cardiac arrhythmia adverse event that may have occurred has resolved to ≤ grade 1 severity;
- Any other lenalidomide-related adverse event that may have occurred has resolved to \leq grade 2 severity.

If these conditions are not met on Day 1 of a new cycle, the subject will be evaluated weekly and a new cycle of lenalidomide will not be initiated until the toxicity has resolved as described above. If lenalidomide dosing was omitted during the previous cycle and was restarted with a one-level dose reduction without requiring an interruption for the remainder of the cycle, then that reduced dose level will be initiated on Day 1 of the new cycle. If lenalidomide dosing was omitted for the remainder of the previous cycle or if the new cycle is delayed due to toxicity newly encountered on the scheduled Day 1, then the new cycle will be started with a one-level dose reduction.

If either drug is discontinued, patient will come off treatment and go to event monitoring.

| → → Use the NCI Common Terminology Criteria for Adverse Events (CTCAE) version 4.0 unless otherwise specified $\leftarrow \leftarrow$ | | | | |
|---|---|--------------|---|--|
| CTCAE System/Organ/Class (SOC) | ADVERSE EVENT | AGENT | ACTION | |
| | BASED ON INTERVAL | ADVERSE E | EVENTS (Days 2-28) | |
| Investigations | Platelet count decreased*: (Platelets < 10,000/mm ³) | | Omit dose. Follow CBC weekly. If thrombocytopenia resolves to ≤ grade 3 restart lenalidomide at the same dose level. | |
| | | | If thrombocytopenia < 10,000/mm³ recurs, reduce dose by one dose level (5 mg) and continue therapy when platelet count ≥ 25,000/mm³. | |
| | Grade 4 Neutrophil count | | • Omit dose. | |
| | decreased* | | • Follow CBC weekly. | |
| | | Lenalidomide | If neutropenia has resolved to ≤ grade 2, resume dose at same level with GCSF support. | |
| Blood and lymphatic | ≥ Grade 3 Febrile | omi | Omit dose. | |
| system disorders | neutropenia | de | • Follow CBC weekly. | |
| | | | If neutropenia has resolved to ≤ grade 2, resume dose at same level with GCSF support. | |

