| Cardiac Disorders | Sinus bradycardia/ other cardiac Arrhythmia Grade 2 | | Omit dose. Follow at least weekly. If the toxicity resolves to ≤ grade 1, reduce dose by one dose level (5mg) and continue therapy. | |
| | \geq Grade 3 | | • Discontinue study treatment and go to | |
| Vascular disorders | thromboembolic event \geq Grade 3 | | event monitoring. Omit dose and start anticoagulation; restart at investigator's discretion (maintain dose level). | |

| \rightarrow \rightarrow Use the NCI Common Terminology Criteria for Adverse Events (CTCAE) version 4.0 unless | | | |
|---|--|--------------------------|--|
| | otherwise | e specified \leftarrow | F |
| CTCAE System/Organ/Class (SOC) | ADVERSE EVENT | AGENT | ACTION |
| | BASED ON INTERVAL | ADVERSE E | VENTS (Days 2-28) |
| Immune system disorders | Allergic reaction Grade 2-3 | | Omit dose. Follow at least weekly. If the toxicity resolves to ≤ grade 1, reduce dose by 5 mg and continue therapy. |
| Anaphylaxis Grade 4 | | | • Discontinue study treatment and go to event monitoring. |
| | Erythema multiforme ≥ Grade 3 | Г | • Discontinue study treatment and go to event monitoring. |
| Skin and | Skin ulceration \geq Grade 2 | Lenalidomide | • Discontinue study treatment and go to event monitoring. |
| subcutaneous tissue disorders | Other: Non-blistering rash Grade 3 | | If Grade 3 omit dose. Follow weekly. If the toxicity resolves to ≤ grade 2 continue therapy. |
| | Other: Non-blistering rash Grade 4 | | • Discontinue study treatment and go to event monitoring. |
| Other | Non-hematologic toxicity assessed as lenalidomide related ≥ Grade 3 | | Omit dose. Follow at least weekly. If the toxicity resolves to ≤ grade 2, implement one dose reduction step and continue therapy. |

* use IWCLL/Hallek, December 2008 criteria (see Appendix V)

NOTE: Subjects who cannot tolerate the minimum dose 5 mg daily on days 1 - 21 of a 28 day cycle, are to be discontinued from the treatment phase of the study and go to event monitoring.

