Note: Dose modification schedule as outlined in the table above will be applicable to all patients enrolled on the study. This schedule will not be applicable to patients during the two cycles of the combination therapy of the patients enrolled on the phase I portion of the study to clearly define MTD. Once patients on the phase I portion of the study have completed cycle #2 (1st combination cycle) they may be managed based on the dose modification criteria outlined in the table above. Dose modification due to toxicity will be based on dose de-escalation in 5 mg increments from the maximum dose obtained for the individual patient. The optimum dose in any individual patient may be determined by the investigator based on managing toxicity and maximizing response. The maximum dose of lenalidomide permitted will not exceed the MTD determined in the phase I portion of the study and is not to exceed 20 mg daily on days 1 - 21 of a 28 day cycle and the minimum dose permitted is 5 mg daily on days 1 - 21 of a 28 day cycle.

Dose re-escalation: For patients who are dose reduced either for disease or drug related toxicities, lenalidomide dose re-escalation can be considered provided all toxicity has resolved to \leq Grade 1. Patients can be started at minimum of 5mg PO daily on days 1 - 21 of a 28 day cycle and the dose titrated up at 5mg increments weekly to the target dose not to exceed the MTD determined in the phase I portion of the study. The rate of escalation is at the PI discretion based on patient tolerability and concern for tumor lysis syndrome.

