 - 16.21 MTD Definition: MTD is defined as the dose level below the lowest dose that induces dose-limiting toxicity (DLT) in at least one-third of patients (at least 2 of a maximum of 6 new patients). A total of 6 patients treated at the MTD will be sufficient to identify common toxicities at the MTD. For instance, those toxicities with an incidence of at least 25% will be observed with a probability of at least $82\% (1-(1-0.25)^6)$.

Refer to Section 7.24 for definition of dose-limiting toxicity (DLT).

16.22 MTD Determination:

Dose Escalation: The phase I portion of this study will utilize a standard cohort of three design. The dose levels to which patients will be assigned in sequential cohorts are described in Section 7.1. The first cohort of three patients will be

treated at dose level 1. Decisions on when and how to dose escalate are described below.

- 16.221 Three patients will be treated at a given dose level combination and observed for at least 2 cycles from start of treatment to assess toxicity.
- 16.222 If DLT is not seen in any of the 3 patients, 3 new patients will be accrued and treated at the next higher dose level. If DLT is seen in 2 or 3 of 3 patients treated at a given dose level, then the next 3 patients will be treated at the next lower dose level, if only 3 patients were enrolled and treated at this lower dose level.
- 16.223 If DLT is seen in 1 of 3 patients treated at a given dose level, up to 3 additional patients will be enrolled and treated at the same dose level. If DLT is seen in at least one of these additional three patients (≥2 of 6), the MTD will have been exceeded and further accrual will cease to this cohort. If dose-limiting toxicity (DLT) is not seen in any of the three additional patients, 3 new patients will be accrued and treated at the next higher dose level.
- 16.224 After enrolling 6 patients on a specific dose level, if DLT is observed in at least 2 of 6 patients, then the MTD will have been exceeded and defined as the previous dose unless only 3 patients were treated at the lower dose level. In that case, 3 additional patients will be treated at this lower dose level such that a total of 6 patients are treated at the MTD to more fully assess the toxicities associated with the MTD.

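### DLTs are counted only in cycle 2, so cycle 1 toxicity on the escalated drug does not enter the MTD decision, and the plan does not say how to score a patient who stops in cycle 1 or starts cycle 2 below the assigned dose

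*Combined protocol and SAP*

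**What the plan says.** **Treatment.** In 7.21, levels 1 to 4 hold AT-101 at 40 mg b.i.d. and raise lenalidomide through 5, 10, 15 and 20 mg. In 7.11, cycle 1 is lenalidomide alone on days 1-21, at a dose given as "As assigned by Registration Office". AT-101 joins in cycle 2. In 7.12, phase II patients receive the MTD of lenalidomide from cycle 1.

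**DLT window.** In 7.221 a DLT is a related event that "occurs in cycle 2 of the study treatment" and meets the listed criteria. In 7.212 each cohort of three is "observed during the first cycle of the combination therapy". In 16.221 the cohort is "observed for at least 2 cycles from start of treatment to assess toxicity".

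**Non-completers.** Section 13.3 replaces a phase I patient who does not finish two cycles for any reason except toxicity. Section 16.226 replaces one who does not finish for any reason except a DLT. It keeps the toxicity data for analysis, but not for the escalation rule.

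**Dose at the start of cycle 2.** In the 8.2 table, a related non-hematologic toxicity of grade 3 or more that settles leads the site to "implement one dose reduction step and continue therapy". Where lenalidomide was omitted and restarted one level down, "then that reduced dose level will be initiated on Day 1 of the new cycle". A note to 8.2 then says of phase I: "This schedule will not be applicable to patients during the two cycles of the combination therapy". Its next sentence allows management by the table once cycle 2 is complete. A note in 8.3 bars dose reduction in cycle 2, and 7.11 gives the lenalidomide dose for cycles 2-12 as the one assigned at registration.

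**The concern.** The escalation decision is meant to judge a lenalidomide dose, yet the first 28 days on that dose lie outside the window. Febrile neutropenia attributed to treatment is a DLT in cycle 2; the same event at the same dose in cycle 1 is not. A patient who comes off treatment for it (13.1 provides for unacceptable adverse events) leaves the denominator under 16.226. The level can then be cleared on the patients who tolerated cycle 1.

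The MTD is the phase I primary endpoint. It is carried to up to 31 further evaluable patients, who take it from cycle 1, and the six phase I patients at the MTD enter the phase II analysis (16.12). The phase II stopping rule in 16.52 is not a full backstop: it counts only non-hematologic events of grade 4 or higher, so it would not register grade 3 non-hematologic or any hematologic toxicity.

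**Working it through.** **1. Reproduce the plan's table.** Under the cohort-of-three rule a level is cleared with 0 of 3 DLTs, or with 1 of 3 followed by 0 of 3:

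P(escalate) = (1-p)³ + 3p(1-p)²·(1-p)³ = (1-p)³ + 3p(1-p)⁵

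For p = 10, 20, 30, 40 and 50% this gives 0.906, 0.709, 0.494, 0.309 and 0.172. All five agree with 16.227 (0.91, 0.71, 0.49, 0.31, 0.17). The table is correct; the issue is which p goes into it. Under 7.221, p is the cycle 2 rate alone.

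**2. Direction.** P(escalate) falls as p rises. Adding cycle 1 events can only raise p, so leaving them out can only raise P(escalate) relative to a two-cycle count.

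**3. Illustration of size.** The documents give no cycle 1 rate. Assume a cycle 1 rate c of DLT-type events, independent of cycle 2, and a cycle 2 rate p₂. The two-cycle rate is 1-(1-c)(1-p₂).

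| p₂ (assumed) | c (assumed) | Two-cycle rate | P(escalate) as written | P(escalate), both cycles counted |
|---|---|---|---|---|
| 10% | 10% | 1-0.9×0.9 = 19% | 0.91 | 0.73 |
| 10% | 20% | 1-0.8×0.9 = 28% | 0.91 | 0.54 |
| 10% | 30% | 1-0.7×0.9 = 37% | 0.91 | 0.36 |
| 20% | 10% | 1-0.9×0.8 = 28% | 0.71 | 0.54 |
| 20% | 20% | 1-0.8×0.8 = 36% | 0.71 | 0.38 |

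Example at 19%: 0.81³ + 3(0.19)(0.81)⁵ = 0.531 + 0.199 = 0.730.

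**4. Patient who stops in cycle 1 for a DLT-type event.**

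| Section | Consequence |
|---|---|
| 7.221 | Not a DLT, because it is not in cycle 2 |
| 16.226 | Reason is not a DLT as defined, so uninformative and replaced |
| 13.3 | Reason is toxicity, so the replacement rule does not apply |

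Under 13.3 the patient is neither replaced nor a DLT, and no section gives a status.

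**5. Patient reduced in cycle 1.** The Day 1 rules in 8.2 would start cycle 2 at the lower level. The exemption in the 8.2 note refers to combination cycles, which cycle 1 is not. Its next sentence, the note in 8.3 and the dose table in 7.11 all point to no reduction before or in cycle 2. The passages do not settle the matter. Under 16.222-16.226, a patient who completes two cycles without a cycle 2 DLT counts as DLT-free at the assigned level, because nothing says otherwise.

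If this path operates, suppose a share f of patients takes cycle 2 one level down. The effective rate is (1-f)p + f·p_lower. With assumed rates of 40% at the assigned level and 25% one level down, f = 20% gives 0.8×0.40 + 0.2×0.25 = 37%, and P(escalate) moves from 0.31 to 0.36. That is the same direction, and smaller than most of the effects in step 3.

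**The case against.** The cycle 2 window looks deliberate. Goal 2.11 is to "Determine the maximum tolerated dose (MTD) of lenalidomide in combination with AT-101", cycle 2 is the first combination cycle, and 7.212, 7.221 and 8.3 all treat it as the defining cycle. The rationale in Section 1.0 reports earlier single-agent use at 25 mg/day, calls 20 mg/day the most tolerable dose in hematologic terms, and caps the study there. On this view, counting lead-in events changes what the MTD describes rather than correcting an error. That stands as an explanation of the choice. It does not explain why 16.221 asks for two cycles of observation, why a patient lost to cycle 1 toxicity is replaced, or how an MTD defined without cycle 1 supports a phase II regimen that starts with it.

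A reader might infer that patients reduced in cycle 1 do enter cycle 2 below their level and are recorded as tolerating it. The documents do not establish this. The sentence after the exemption in 8.2, the note in 8.3 and the table in 7.11 support the opposite reading, and scoring as DLT-free is a default from silence. Even under the Day 1 rules the path is narrow. First platelet and neutrophil events restart at the same dose unless dosing is omitted for the rest of the cycle or the next cycle is delayed, several rows of the table end treatment, and at 5 mg there is no lower lenalidomide level.

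A reader might also set the 37% in the illustration against the one-third limit in 16.21. That limit applies to DLTs as the plan defines them, so 37% does not show that it would be breached.

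**Conclusion.** The point holds for the DLT window and for non-completers. Cycle 1 toxicity on the escalated drug cannot count against a level, and 16.226 replaces the patient who stops for it, in conflict with 13.3. Relative to a two-cycle count, which is what the phase II regimen calls for, the effect is toward escalation. Its size cannot be derived from the documents. The contrast of 0.91 with 0.73, 0.54 or 0.36 rests on an assumed 10% cycle 2 rate, assumed cycle 1 rates of 10-30%, and independence between cycles; with a cycle 1 rate near zero the difference vanishes.

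The dose at the start of cycle 2 is an unresolved contradiction with no scoring rule, not a demonstrated bias. It needs clarifying but carries less weight than the window and replacement rules.

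**What to change.** - In 7.221 and 16.221-16.226, count an event that meets the DLT criteria in cycle 1 or cycle 2 as a DLT at the assigned level. A patient who stops in cycle 1 for such an event then counts as a DLT and is not replaced.
- Count a patient as DLT-free at a level only if cycle 2 was started at the assigned dose. A patient who started lower and had no DLT is not evaluable for that level.
- Reconcile 13.3 with 16.226, and 7.212 with 16.221.
- Reconcile 7.11, the Day 1 rules and phase I note in 8.2, and the note in 8.3, so that it is clear what a phase I patient may receive in cycle 2. This point takes no position on which dose or dose-modification rule should apply.

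The formula and table in 16.227 stay as they are; p becomes the two-cycle rate.

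The cost is a short amendment across several sections. Escalation may stop at a lower level, and an occasional replacement patient may be needed. Growth factors are barred only in cycle 2 (7.11, 9.2), so neutrophil events in the two cycles are not strictly comparable; cycle 1 events should be reported with growth factor use noted.
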